1. ABBREVIATIONS

AE	Adverse Events
BMI	Body Mass Index
C + I	casirivimab + imdevimab
CDC	Centers for Disease Control and Prevention
COPD	Chronic Obstructive Pulmonary Disease
COVID-19	Coronavirus disease 2019
CVD	Cardiovascular Disease
EUA	Emergency Use Authorization
FDA	Food and Drug Administration
HHS	Health and Human Services
HFD	Hospital Free Days
HTN	Hypertension
kDa	Kilodaltons
IgG1	Immunoglobulin G1
KG	Kilograms
OPTIMISE-C19	OPtimizing Treatment and Impact of Monoclonal antibodies through Evaluation
mAb	Monoclonal Antibodies
PCR	Polymerase Chain Reaction
SAEs	Serious Adverse Events
SARS-CoV-2	Severe Acute Respiratory Syndrome Coronavirus 2
UATRC	UPMC Antibody Treatment and Evaluation Center
Vir-7831	sotrovimab

2. BACKGROUND and RATIONALE

3. BACKGROUND

While COVID-19 vaccination will reduce COVID-19-related morbidity and mortality, the learned immune response may vary between individuals. This means interventions such as monoclonal antibodies (mAb) will still be needed to prevent progression of COVID-19 illness. Monoclonal antibodies seek to mimic or enhance the natural immune system response against a pathogen and are often used in the care of patients with cancer or infection.

For viral infections, mAbs are created by exposing a white blood cell to a particular viral protein, which is then cloned to mass produce antibodies to target that virus. For SARS-CoV-2, the virus that causes COVID-19, IgG1 mAbs target the spike protein of SARS-CoV-2 and block viral attachment and entry into cells.

The SARS-CoV-2 mAbs bamlanivimab and etesevimab, and the REGN-COV2 combination (casirivimab + imdevimab) reduce nasopharyngeal viral burden plus clinical outcomes including future emergency department visits and hospitalizations (Weinreich 33332778, NEJM, Gottlieb 33475701). Each received FDA Emergency Use Authorization (EUA) for use in selected populations (**Exhibit**); in April 2021 FDA revoked the EUA for bamlanivimab monotherapy, and in June 2021 FDA recommended bamlanivimab and etesevimab not be used. Additional trials of pre-exposure prophylaxis (NCT04497987) and other applications are underway, and additional mAbs are in development.

In May 2021, it was announced that sotrovimab demonstrated clinical efficacy (85%) in reducing hospitalizations for more than 24 hours or death in those that received sotrovimab as compared to placebo (NCT04545060). Subsequently, it received EUA approval in select populations. Additional trials are underway.

The trials demonstrated the greatest impact of the REGN-COV2 dual therapy among patients who lacked neutralizing antibodies against SARS-CoV-2 at baseline and in those with high nasopharyngeal viral loads. Additionally, few patients in the bamlanivimab/etesevimab trial developed treatment-emergent SARS-CoV-2 resistance. This latter phenomenon may further enhance the need for therapies given the recent emergence of SARS-CoV-2 variants that may escape vaccination. However, the relative effectiveness of each mAb compared to the other is unknown, as is their effectiveness for emerging virus variants.

This Appendix to the UPMC Pilot Core (PittPro 20040210) describes the approach of the UPMC OPTIMISE-C19 evaluation. We will conduct a pragmatic evaluation of monoclonal antibody treatments in participants with COVID-19 illness, starting with the patient population approved under the current FDA mAb EUAs.

4. RATIONALE

As of June 2021, there are over 10,000 new cases of COVID-19 diagnosed daily in the US https://covid.cdc.gov/covid-data-tracker/#trends_dailytrendscases, with over 1500 daily COVID-19 related hospital admissions Microsoft Power BI (powerbigov.us). Although case volumes are currently declining, COVID-19 remains a significant public health threat.

Despite the EUAs, the clinical use of mAbs is low due in part to lack of patient access, complexities in drug allocation, and lack of knowledge among providers are contributing factors. Further, the comparative effectiveness of different mAbs is unknown and not yet directly studied. The National Academies of Sciences, Engineering, and Medicine recently called for expanded access and clinical use of mAbs, noting it is “critical to collect data and evaluate whether they are working as predicted.”

This evaluation seeks to expand access to mAbs at UPMC and determine their relative effects versus each other, starting with those governed by EUAs.

5. OBJECTIVES AND METRICS

6. OBJECTIVES

The primary objective is to evaluate the clinical and biological effect of multiple monoclonal antibodies (mAbs) in patients with COVID-19.

The primary hypothesis is clinical and biological effect will vary between mAbs, by SARS-CoV-2 variants, and patient characteristics.

7. METRICS

The primary evaluation metric is total hospital free days (HFD) at 28 days after mAb receipt calculated as 28 minus the number of days during the index stay minus the number of days readmitted during the 28 days after treatment. Death within 28 days is recorded as -1 HFD.

Secondary evaluation metrics include:

- All-cause and all-location mortality at 28 and 90 days
- Emergency department visits at 28 days
- Organ-support free days at day 28
- Where feasible:
 - SARS-CoV-2 nasopharyngeal and plasma viral loads among participants from baseline and longitudinally through day 28
 - SARS-CoV-2 antibody titers, antibody neutralization, and other immune responses at baseline and longitudinally through day 28
 - Detection of SARS-CoV-2 variants through next-generation sequencing at baseline and longitudinally through day 28
 - Determining the duration of SARS-CoV-2 infectivity and non-culture surrogates for SARS-CoV-2 infectivity among patients with persistent nasopharyngeal swab viral shedding

8. DESIGN

We will conduct a pragmatic evaluation of participants with COVID-19 illness under existing UPMC processes for the clinical care of COVID-19 positive patients, including EUA requirements for mAb administration. A patient who presents to a UPMC facility and tests positive for COVID-19 will, as per current common care, be offered monoclonal antibodies. Data that are already collected according to UPMC procedures and EUA requirements are used for analysis.

9. POPULATION

We will evaluate patients that present to UPMC Emergency Departments, urgent care sites, infusions centers and other facilities that can or do provide mAbs for COVID-19. As of June 30, 2021, there are 2 EUAs for COVID-19 mAbs, with common inclusion and exclusion criteria, and we will evaluate patients that meet these criteria. As FDA antibody decisions change (E.g., FDA revokes or grants EUAs, or changes eligibility criteria), eligibility criteria will change.

10. INCLUSION CRITERIA

As per the current EUA criteria (June 2021), the following patients are included:

- Adult (≥ 18 years old)
- Children ≥ 12 years old weighing at least 40 kg
- With a positive SARS-CoV-2 antigen or PCR test and within 10 days of symptom onset
- High risk of disease progression

High risk is defined as patients who meet at least one of the following criteria:

- Are ≥ 65 years old
- A Body Mass Index (BMI) >25 , or if age 12–17, BMI $\geq 85^{\text{th}}$ percentile
- Pregnancy
- Have chronic kidney disease
- Have diabetes
- Have immunosuppressive disease
- Are currently receiving immunosuppressive treatment
- Cardiovascular disease (including congenital heart disease) or hypertension
- Chronic lung disease
- sickle cell disease
- neurodevelopmental disorders (e.g., cerebral palsy) or other conditions that confer medical complexity (e.g., genetic, or metabolic syndromes and severe congenital anomalies)
- a medical-related technological dependence, for example, tracheostomy or gastrostomy)

The EUAs note that other medical conditions or factors (for example, race or ethnicity) may also place individual patients at high risk for progression and authorization of mAb treatment under the EUA is not limited to the medical conditions or factors listed above.

11. EXCLUSION CRITERIA

As per the current EUA criteria (June 2021), the following are excluded:

- Are hospitalized for the treatment of COVID-19
- Require oxygen therapy for the treatment of COVID-19
- Require an increase in baseline oxygen flow rate due to COVID-19 in those on chronic oxygen therapy due to underlying non-COVID-19 related comorbidity
- Have a known hypersensitivity to any antibody ingredient

12. EVALUATED TREATMENTS

We will evaluate mAbs governed by FDA EUAs. Patients will receive COVID-19 mAbs governed by FDA EUAs, when their treating physician orders a mAb and they meet EUA criteria. As FDA antibody decisions change (e.g., FDA revokes or grants EUAs, provides full approval, or changes eligibility criteria), available evaluated treatments

will change. In April 2021, FDA revoked the EUA for bamlanivimab monotherapy and in June 2021 FDA recommended bamlanivimab and etesevimab not be used.

As of June 30, 2021, the EUA-approved mAbs are as listed below.

13. CASIRIVIMAB and IMDEVIMAB

Casirivimab, a human immunoglobulin G-1 (IgG1) monoclonal antibody (mAb), is covalent eterotetramer consisting of 2 heavy chains and 2 light chains produced by recombinant DNA technology in Chinese hamster ovary (CHO) cell suspension culture and has an approximate molecular weight of 145.23 kDa.

Imdevimab, a human IgG1 mAb, is a covalent heterotetramer consisting of 2 heavy chains and 2 light chains produced by recombinant DNA technology in Chinese hamster ovary (CHO) cell suspension culture and has an approximate molecular weight of 144.14 kDa.

14. SOTROVIMAB

Vir 7831 (sotrovimab) is a recombinant human IgG1k monoclonal antibody that binds to a conserved epitope on the spike protein receptor binding domain of SARS-CoV-2. Sotrovimab does not compete with human ACE2 receptor binding.

15. CONCOMITANT THERAPY

All care and concomitant therapy are as per the treating providers.

16. CONDUCT

17. DATA COLLECTION

The EUAs require that healthcare facilities and providers report therapeutic information and utilization data through HHS Protect, Teletracking, or National Healthcare Safety Network as directed by the US Department of Health and Human Services.

We will collect data including baseline demographics and underlying conditions, results of SARS-CoV-2 PCR or antibody testing, and initial care including mAb infusion completion. We will collect post-randomization healthcare encounters, including hospitalization, emergency department visits, ICU care, and other measures of healthcare utilization. We will use an electronic health record data collection process to augment existing UPMC data collection processes, as necessary.

All data will be handled and secured as per University of Pittsburgh and UPMC data guidelines.

There will be no research activities involving direct interaction with subjects performed as part of this evaluation.

In addition to the primary and secondary outcome data referenced in this submission, data collected will include the below areas. All data will be abstracted directly from the electronic health record and handled anonymously.

- mAb was administered, including date, time, and infusion completion as well as the location of the infusion
- Demographics (including age, sex, race, body weight, vaccination status)
- Healthcare encounters, including hospital and ICU admission status if applicable
- Medication usage and doses
- Hospital and ICU admission status, if applicable
- Administration of medications related to COVID-19, if applicable
- Remnant blood availability
- Laboratory and microbiology data, including COVID-19 testing done for clinical purposes

18. BIOSPECIMENS

Where feasible, we will collect discarded remnant blood samples and nasal/oropharyngeal swab samples to quantify the viral load and host response to the virus. As noted under data collection, we will record laboratory and microbiology data performed for clinical purposes.

19. ANTIBODY ADMINISTRATION

Antibodies will be administered as per the EUAs, UPMC Pharmacy and Therapeutics policies and the respective Pharmacy Manuals (as generated by the pharmaceutical companies), if applicable. Providers will explain mAb risks and benefits and provide the EUA Fact Sheets for Patients, Parents and Caregivers as per EUA requirements.

20. mAb assignment

The COVID-19 mAbs are currently routinely used at UPMC. Once any order for mAb infusion is approved by the UPMC system oversight group, the pharmacy provides whichever EUA-governed mAb is available under a therapeutic interchange approach. Ordering physicians review with the patient the EUA Fact Sheet for each mAb and explain that the patient could receive any of the mAbs governed by FDA EUAs.

If demand for mAb exceeds supply, UPMC has a lottery system to allot who receives the therapy once requested by a physician.

Our current proposal is a UPMC system quality improvement initiative, embracing and extending the current lottery system and therapeutic interchange policy for EUA-governed mAbs for COVID-19 as follows:

1. The Physician orders mAb.

a. If scarcity present and lottery system allow provision, proceed.

2. The Pharmacy fills order with one of the EUA-governed COVID-19 mAbs using an embedded assignment system akin to current mAb provision. This system will allow a comparative effectiveness evaluation of the multiple mAbs by effectively ensuring random allocation.

3. The Physician can agree to the assigned mAb or can request a specific mAb.

It is the treating physician's choice to accept the assigned mAb or not, and therefore patient consent for the mAb assignment is not required. Patients will be told which mAb they are receiving, along with an EUA Fact Sheet, as per EUA requirements.

21. STATISTICAL CONSIDERATIONS

22. STRATA

Predefined strata will include patients discharged home after infusion, patients admitted to hospital after infusion, prior vaccination, and if known, presence of virus variants of concern at baseline and presence of neutralizing antibodies to SARS-CoV-2 at baseline.

23. NUMBER of PARTICIPANTS

Sample size is determined by case volume throughout the course of the pandemic.

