### Primary Endpoint

The primary endpoint in the trial is hospital-free days (HFDs). The endpoint is a composite of death and number of days alive and free of the hospital. The worst outcome is that a patient dies within 28 days. This outcome is labeled as  $a-1$  HFDs. For patients who do not die within 28 days the primary endpoint is the number of days alive and free of hospitalization. For patients alive at day 28 the endpoint is characterized as an integer value with the number of days free of hospital admission, with possible

values 0, 1, 2, 3, ..., 28. For statistical analyses the endpoint is modeled as an ordered categorical variable. If a patient has intervening days free of hospital and then has a re-hospitalization the patient will be given credit for the intervening days as “free” of the hospital.

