### 2. Post hoc subgroup analyses

- By symptom onset (>5 days or  $\leq 5$  days)
- By location (0=infusion center, 1=ED)

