The primary endpoint in the trial is hospital-free days (HFDs). The endpoint is a composite of death and number of days alive and free of the hospital. The worst outcome is that a patient dies within 28 days. This outcome is labeled as a -1 HFDs. For patients who do not die within 28 days the primary endpoint is the number of days alive and free of hospitalization. For patients alive at day 28 the endpoint is characterized as an integer value with the number of days free of hospital admission, with possible values $0, 1, 2, 3, \dots, 28$. For statistical analyses the endpoint is modeled as an ordered categorical variable. If a patient has intervening days free of hospital and then has a re-hospitalization the patient will be given credit for the intervening days as “free” of the hospital.

Primary Analysis Population

The primary analysis population, used for all adaptive analyses is the “As-Infused” population. The intent-to-treat population includes all patients randomized to an mAb arm. The “as-infused” population includes those patients that show up and are infused for their mAb. Given that all arms are a mAb arm, there is no anticipated relationship between lack of infusion and the assigned arm. Hence all adaptive analyses and safety analyses will be based on the as-infused population (where patients are coded by the mAb arm they receive). Patients who receive a randomized mAb allocation and are not infused may be tracked as a real-world evidence arm of outcome for a non-mAb control (see secondary analyses).

Primary Analysis Model

The primary analysis model for the primary endpoint is a cumulative proportional odds model. Let the probability of an outcome of less than or equal to y be $\pi_y = \Pr(Y \leq y)$. Let a be the indicator of treatment arm ($a=1,\dots,k$). The model adjusts for the following baseline variables:

1. ED or infusion center (0=infusion center, 1=ED)
2. Age (with categories of <30, 30-39, 40-49, 50-59, 60-69, 70-79, and ≥ 80 ; 60-69 will be used as the referent)
3. Sex (sex at birth, male is the referent)
4. COVID-19 variant (0=unknown/uncollected (referent), categorical endpoint for each known variant)
5. Time (two-week epochs of time are used for adjustments; the most current 4-week period is the referent)

The primary analysis model is based on a cumulative logistic regression, where $\pi_y = \Pr(Y \leq y)$, where

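### Protocol section 22 predefines strata by disposition after infusion, which is a component of the primary endpoint; arm comparisons within them would be biased if the arm changes who is admitted

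*Combined protocol and SAP*

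**What the plan says.** Protocol section 22 reads: "Predefined strata will include patients discharged home after infusion, patients admitted to hospital after infusion, prior vaccination". The same sentence adds, if known, "presence of virus variants of concern at baseline and presence of neutralizing antibodies to SARS-CoV-2 at baseline". Vaccination is therefore prior to treatment, and variant and antibody status are fixed at baseline. Only the home/admitted pair is defined by something that happens after infusion. The section does not say what the strata are for, or whether disposition means the immediate outcome of the infusion visit or any admission up to day 28.

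Protocol section 7 defines the primary metric, HFD, as "calculated as 28 minus the number of days during the index stay minus the number of days readmitted during the 28 days after treatment", and adds "Death within 28 days is recorded as -1 HFD". The SAP, under Primary Endpoint, agrees: "The endpoint is a composite of death and number of days alive and free of the hospital". Protocol section 11 excludes patients who "Are hospitalized for the treatment of COVID-19".

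The SAP gives two ways to analyse a subgroup. Modeling Treatment Heterogeneity adds the subgroup to the model and estimates a treatment effect at each level. Subgroup Analyses in the October 28, 2021 read-out fits the model separately in each level. That read-out names vaccine status as its only a priori subgroup and attributes this to the approved protocol. Among its post hoc subgroups it lists "By location (0=infusion center, 1=ED".

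**The concern.** Randomization makes the arms comparable at assignment. It does not make the admitted patients of one arm comparable with the admitted patients of another when the arm influences admission. An arm that prevents the milder admissions leaves a sicker group in its admitted stratum, and it may leave higher-risk patients in its home stratum. Comparing arms inside either stratum then mixes the drug effect with this selection. Assignment is open-label, so disposition can also be decided with the arm known.

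The word predefined carries weight. Prior vaccination is a section 22 stratum, and the October 2021 read-out gives it a priori status by reference to the protocol. By the same route, a later read-out could present home/admitted comparisons as prespecified, and readers would give them more trust than they deserve.

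**Working it through.** The documents give no admission rates, sample size or effect size for this point, so there is no plan figure to reproduce. All rates below are assumptions.

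**Step 1: is disposition part of the endpoint?** Yes. Index-stay days and readmission days are both subtracted from 28, so any counted hospital day after infusion lowers HFD.

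**Step 2: a hand calculation.** Assume that everyone not admitted has HFD = 28.

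- Arm 1: 12% admitted (9% mild, 3% severe).
- Arm 2: 9% admitted (6% mild, 3% severe). This prevents 3/12 = a quarter of all admissions and 3/9 = a third of mild ones.
- All patients, OR for HFD = 28: (0.91/0.09)/(0.88/0.12) = 10.11/7.33 = **1.38**, favouring arm 2.
- Admitted stratum, OR for a non-severe course: (6/3)/(9/3) = 2/3 = **0.67**, against arm 2.

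These two ORs concern different outcomes. On the outcome used in the second, the arms are identical overall (3% severe in each, OR 1.00), so the 0.67 comes entirely from who is left in the stratum.

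**Step 3: the full HFD scale.** A two-arm proportional-odds model was fitted to expected HFD distributions. An OR above 1 favours arm 2. Three patient types were assumed:

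- Admitted under either arm: HFD -1, 8, 14, 20 with probabilities 0.15, 0.25, 0.30, 0.30.
- Admitted under arm 1 only: HFD 18, 22, 24, 26 with probabilities 0.1, 0.3, 0.4, 0.2 under arm 1. Under arm 2, on the immediate reading: HFD 20, 24, 25, 28 with probabilities 0.05, 0.10, 0.15, 0.70.
- Home under either arm, immediate reading: HFD 24 or 28 with probabilities 0.03 and 0.97.

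On the day-28 reading, every patient in the home stratum is given HFD 28.

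| Admitted under both arms / arm 1 only | Immediate: overall | Immediate: admitted | Immediate: home | Day-28: overall | Day-28: admitted |
|---|---|---|---|---|---|
| 5% / 2% | 1.18 | 0.42 | 0.84 | 1.41 | 0.42 |
| 5% / 5% | 1.42 | 0.20 | 0.67 | 2.04 | 0.20 |
| 8% / 4% | 1.26 | 0.36 | 0.71 | 1.51 | 0.36 |
| 3% / 1% | 1.12 | 0.47 | 0.91 | not run | not run |

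In the first row on the immediate reading, mean HFD is 26.99 against 27.07 overall (arm 2 better), 15.2 against 12.1 among the admitted, and 27.88 against 27.86 at home. In all four immediate-reading rows arm 2 is better overall and looks worse in both strata. On the day-28 reading the home stratum shows no contrast, because surviving home patients have HFD 28 in both arms.

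**Step 4: when it does not reverse.** Let 7% be admitted in both arms, with the arm not affecting who they are, and give arm 2 a better hospital course (HFD -1, 8, 14, 20 with probabilities 0.10, 0.20, 0.30, 0.40). The ORs are 1.56 among the admitted, 1.00 at home and 1.01 overall, so the direction is preserved.

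**The case against.** The strongest reply is that nothing planned uses this stratum. Protocol section 24 leaves the analysis to the SAP, and neither SAP version specifies a comparison by disposition. The primary model adjusts for care location, age, sex, variant and time (the read-outs drop variant). The July 2021 read-out estimates separate effects by time epoch only. This stands. A reader might infer that the primary analysis or the adaptive machinery is compromised, and the documents do not support that. Nor do they call any subgroup confirmatory.

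A second reply is that the wording reads naturally as disposition from the infusion visit, since section 7 separates the index stay from readmission. On that reading disposition largely reflects severity at presentation, and the antibody has little time to alter it. This stands as a reason why the risk may be small. It does not remove the risk, because the protocol does not define the term and care is open-label.

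A reader might also infer that every admitted patient has already had the study event. Section 11 excludes only patients in hospital for the treatment of COVID-19, not those in hospital for another reason, so that goes too far.

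Finally, a reader might infer that the October 2021 read-out mislabels location as post hoc. It does not. The read-out plan was created on November 4, 2021, after the October 28 data freeze and the September 30 read-out, so the label is accurate. Location is also a different variable from disposition.

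**Conclusion.** The point holds as a defect in prespecification. Section 22 gives predefined status to a grouping that is determined after assignment and forms part of HFD. The primary OR, the inferiority and equivalence triggers and the response-adaptive allocation are unaffected.

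If the strata were analysed as the SAP's subgroup methods provide, the arm comparisons would be biased whenever the arm changes who is admitted. Under the assumed rates, a true advantage of 1.12 to 1.42 overall (immediate reading) became 0.20 to 0.47 among the admitted and 0.67 to 0.91 among those sent home. These figures show that reversal is possible. They do not estimate its size in this trial, because they rest on invented admission rates and stay lengths and on the prevented admissions being the milder ones. Without an arm effect on admission there is no reversal.

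**What to change.** In protocol section 22, remove the two disposition strata as subgroups for arm comparisons. Replace them with care setting at treatment, coded as infusion center or ED. Add observation status only if it can be coded: the protocol change history shows such patients entering from April 2021, but the model's location variable has only two levels.

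If disposition is still reported, define whether it means the immediate outcome of the visit or any admission to day 28. State that it is descriptive only, with no arm effect estimated within it.

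Apply the predefined status of care setting to future read-outs only. Leave the October 2021 location subgroup labelled post hoc, because relabelling it would misstate when it was chosen.

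The cost is a short protocol amendment. Infusion center versus ED is already a model covariate and needs no new data; observation status would need an extra code.
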